Evidence that the toxicity rate is excessive will be considered sufficient if the lower limits of the 90% one-sided confidence intervals for the estimates of the true toxicity rates exceed the toxicity limits defined above (i.e., 20% for Grade 3 events and 10% for Grade 4 events), after the first 5 patients have been accrued. Operationally, this will occur if any of the following events occurs within a study arm: Grade ≥ 3 events (or Grade >1 autoimmune events) are present in at least 3 out of 5, 4 out of 9 (or less), 5 out of 13 (or less), or 6 out of 15 (or less) of the subjects accrued (within a study arm). Furthermore, accrual will be temporarily suspended if any of the following events occur: Grade 4 events are present in at least 2 out of 5, 3 out of 11 (or less), or 4 out of 15 (or less) of the subjects accrued (within a study arm).

If one of these thresholds is reached, accrual will be temporarily suspended and the study will be reviewed by the UW DSMC (data and safety monitoring committee) to consider safety and dose modifications with respect to treatment arm. Once the study is suspended, it would only be reopened if modifications could be made, and approved by the DSMC and the UW-IRB, to assure that patient safety is reestablished. If not, the study would be closed.

B. Endpoints

Patients will come off study at the time of radiographic disease progression, with progression being defined only AFTER the first 3-month staging evaluation, at the time of undue toxicity (as defined below), or at the discretion of the patient and treating physician that other therapies for prostate cancer are warranted. Patients should be discouraged from discontinuing protocol treatment for PSA rise only. Patients will continue to have blood drawn for immune studies, as per study calendar, up to one year after screening, even if off study prior to that time. The 6 month visit, in particular, is important to collect for the purpose of endpoint analysis. Subjects who have not come off study earlier for these reasons will come off study at the end of the one-year treatment period.

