An immune response will be defined based on the detection of augmented numbers of PAP-specific effector (IFN γ -secreting and/or granzyme B-secreting) and/or memory (proliferating) T-cell immune response after immunization, using blood obtained at 6 months for the primary analysis compared with pre-treatment. Specifically, a positive antigen-specific response resulting from immunization will be defined as a PAP-specific response by two or more of these three tests detectable at the 6-month post-treatment time point that is significantly ($p < 0.05$, two-sided using a two-sample t-test) higher than to media only, at least 3-fold higher than the mean baseline value, and with a frequency > 10 per 10^6 PBMC, based on 8-well replicate assays (for ELISPOT-based assays) or triplicate assays (for proliferation analysis). Otherwise, a patient will be declared as an immune non-responder.

Immune response will be determined as a static time point at 6 months, and “durable” immune responses will also be determined by the presence of a PAP-specific immune response by the criteria above detectable at 3, 9, or 12 months after study entry.

C.2. Secondary Clinical and Immunological Endpoints

C.2.1. Time to Progression

Time to progression will be defined as a function of baseline time points in two ways:

- (1) *Time to progression from randomization*: Time elapsed from randomization until disease progression or death. If a patient doesn't experience a disease progression or death event before the end of the follow-up period, then the observation for this patient will be censored.
- (2) *Time to progression from 3 months post-randomization*: Time elapsed from the 3 months disease progression assessment until disease progression or death. If a patient doesn't experience a disease progression or death event before the end of the follow-up period, then the observation for this patient will be censored.

The rationale for defining time to progression as a function of baseline time points (date of randomization and 3-month disease assessment) is described in Section 6 (B).

C.2.2. Twelve-month Progression Free Survival Rate

The 12-month progression free survival rate will be defined as the proportion of patients progression free at the 12 month (post-randomization) disease assessment time point.

C.2.3. Overall Survival

Overall survival will be defined as the time interval from randomization to death from any cause or to the last follow-up in censored patients.

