The number of circulating tumor cells per million PBMC will be summarized in terms of medians and ranges, stratified by study arm and assessment time point. The nonparametric Wilcoxon Signed Rank test will be used to evaluate the effects of treatment on the number of circulating tumor cells within each study arm. The comparison of changes in the number of circulating tumor cells between study arms will be performed using the nonparametric, stratified, Wilcoxon Rank Sum test. Results will be presented graphically over time, and trends (increase, decrease, stable) will be assessed over time.

G.5.2. Analysis for evaluating PAP-specific antibody and T-cell immune responses following treatment with sipuleucel-T and DNA vaccine

PAP-specific antibody and T-cell immune responses, evaluated by multiple different measures described in Section 10.A, following treatment with sipuleucel-T and DNA vaccine will be summarized in tabular format.

G.5.3. Analysis for evaluating whether PAP-specific immune response is associated with prolonged (1 year) progression-free survival

Logistic regression analysis will be conducted to evaluate whether PAP-specific immune response is associated with prolonged (1-year) progression-free survival. The dependent variables will be 12-month progression free survival while treatment arm and PAP-specific immune responses (no vs. yes) will be included as covariates. The results will be reported in terms of odds ratios and the corresponding 95% confidence intervals.

G.5.4. Analysis for evaluating whether baseline immune responses (Th1 type or regulatory type) predict for immune responses elicited/augmented following treatment with sipuleucel-T +/- DNA vaccine

Logistic regression analysis will be conducted to evaluate whether baseline immune responses (Th1-type or regulatory type) predict for immune responses elicited/augmented following treatment with sipuleucel-T +/- DNA vaccine. 6-month and durable immune response at 3,6 or 12 months will be included as dependent variables in this analysis while treatment arm and baseline PAP-specific immune responses (no vs. yes) will be included as covariates. Odds ratios and the corresponding 95% confidence intervals will be reported.

G.5.5. Analysis for evaluating whether treatment elicits immunologic antigen spread to other prostate associated antigens

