The detection of antigen spread to other prostate associated antigens, and the identification of specific antigens recognized, will be analyzed descriptively. In addition, logistic regression analysis will be conducted to evaluate whether antigen spread is associated with the generation

of PAP-specific immune responses elicited as a result of treatment. The dependent variables will be the detection of IgG responses to ≥ 1 “off-target” antigen at 6 months (and not present pre-treatment) while treatment arm and 6-month PAP-specific immune responses (no vs. yes) will be included as covariates. The results will be reported in terms of odds ratios and the corresponding 95% confidence intervals.

13. Administrative Considerations

A. Specimen Handling

Upon entry into the study, each subject will be assigned a unique identification number. All materials collected on that subject will be labeled with that number only, for reasons of confidentiality. Lymphocytes collected will be stored in liquid nitrogen, and sera will be aliquoted and stored at -80°C in the research laboratory of the PI for immune analysis.

B. Institutional Review Board

In accordance with federal regulations (21 CFR 312.66), an Institutional Review Board (IRB) that complies with the regulations in 21 CFR 56 must review and approve this protocol and the informed consent form prior to the initiation of the study at each investigator site. In addition, the study cannot be instituted without FDA approval of the vaccine formulations. Finally, the trial will be conducted with adherence to this protocol, following good clinical practice (GCP) guidelines, and in compliance with other applicable regulatory requirements. Any modifications to the protocol must follow the procedure as outlined in Section 16 below.

C. Consent

The local Principal Investigator, co-investigators, or their associates must explain verbally and in writing the nature, duration, and purpose of the study and possible consequences of the treatment. Patients must also be informed that they may withdraw from the study at any time and for any reason without jeopardizing their future treatment. In accordance with Federal regulations (21 CFR 312), all patients must sign the IRB-approved consent form.

14. Data and Safety Monitoring Plan

A. Oversight and Monitoring Plan

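### Section 12.G.5.3 counts progressions up to month 6 as failures, although the immune-response covariate is by definition a month-6 reading; a month-6 landmark model should carry any biomarker conclusion

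*Combined protocol and SAP*

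**What the plan says.** Section 12.G.5.3 specifies the model: "The dependent variables will be 12-month progression free survival while treatment arm and PAP-specific immune responses (no vs. yes) will be included as covariates". It gives no time point for the response, no analysis set and no landmark. Section 12.G.5.5, by contrast, names the 6-month response explicitly.

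The timing has to be assembled from other sections:

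- **Covariate.** Section 12.C.1 defines immune response "using blood obtained at 6 months for the primary analysis compared with pre-treatment".
- **Outcome.** Section 12.C.2.2 defines the 12-month rate as "the proportion of patients progression free at the 12 month (post-randomization) disease assessment time point". The clock in 12.C.2.1 is "Time elapsed from randomization until disease progression or death".
- **Early events.** Section 6.B states: "Patients will come off study at the time of radiographic disease progression, with progression being defined only AFTER the first 3-month staging evaluation". It also lets patients leave study when other prostate cancer therapy is judged warranted.
- **Sampling after leaving study.** Section 6.B continues: "Patients will continue to have blood drawn for immune studies, as per study calendar, up to one year after screening". Section 9 lets these off-study draws be taken at standard-of-care visits.
- **Evaluability.** Sections 10.A and 12.C.2.6 require a month-6 sample or assessment for a patient to be evaluable for immune response. Section 12.G.5.3 does not refer to that set.

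**The concern.** A patient who progresses between the month-3 staging and month 6 is already a failure when the covariate is read, or becomes one at the same visit. If that patient has left study and started other treatment, the month-6 sample may reflect the progression or its treatment. Section 5.B prohibits systemic corticosteroids and abiraterone, among others, while on study; the documents state no such limit once a patient is off study.

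An odds ratio above 1 could then mean that progression suppressed the response, not that response went with longer PFS. Association of immune response with 1-year PFS is a listed exploratory objective (section 3.C, item 4), and section 2.E says that the trial, if successful, could provide immune biomarkers for the design of future studies. The stake is the reading of that biomarker result. The primary comparison of response rates is not affected.

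**Working it through.** The documents state no figure for this model, so there is none to reproduce. The check asks what odds ratio the model returns when response and progression are truly unrelated.

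**Notation, within one arm**

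- *p*: true response rate. Section 12.F anticipates 25% in Arm 1 and 75% in Arm 2.
- *f*: share with an event by month 6 (assumed).
- *m*: share with an event in months 6-12 (assumed).
- *q*: share of early progressors who would be positive but read negative at month 6 (assumed).

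**Planned model.** Responders remaining among failures are p[m + f(1-q)]; non-responders among failures are (1-p)(m+f) + pfq. The success counts are unaffected. The odds ratio for being progression-free is therefore

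OR = [(1-p)(m+f) + pfq] / {(1-p)[m + f(1-q)]}.

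With q = 0 the numerator and denominator are equal, so OR = 1.

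**Simple illustration.** Take one group with p = 0.5, and let 40% of those event-free at month 6 fail by month 12. For f = 0.20, m = 0.40 × 0.80 = 0.32. With q = 0.5, OR = (0.5 × 0.52 + 0.5 × 0.20 × 0.5) / (0.5 × 0.42) = 0.31/0.21 = 1.48.

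| f | m | OR, q = 0.25 | OR, q = 0.5 |
|---|---|---|---|
| 0.20 | 0.32 | 1.21 | 1.48 |
| 0.30 | 0.28 | 1.30 | 1.70 |
| 0.40 | 0.24 | 1.37 | 1.91 |

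**With the design's response rates, q = 0.5**

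| f | 12-month PFS (assumed) | OR Arm 1 (p = 0.25) | OR Arm 2 (p = 0.75) | Event-free at month 6, of 28 |
|---|---|---|---|---|
| 0.10 | 40% | 1.12 | 1.36 | 25 |
| 0.30 | 40% | 1.44 | 2.33 | 20 |
| 0.50 | 12.5% | 1.53 | 2.60 | 14 |
| 0.75 | 6% | 1.89 | 3.67 | 7 |

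**Affected patients excluded.** If a share q of early progressors is dropped, regardless of their response, the failure share becomes m + f(1-q) among responders and non-responders alike. The OR is again 1.

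**Month-6 landmark.** Only patients event-free at month 6 enter, so f drops out. Failure is m in both groups and OR = 1 for every q.

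**At the planned size.** In 20,000 simulated trials of 14 per arm, with arm and response in the model and a two-sided 0.05 test, false findings in favour of response occurred in about 2-3% of trials at q = 0, 5-12% at q = 0.5 and 8-33% at q = 1. The landmark model gave 1-3%.

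**The case against.** Several points on the other side stand.

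- **The time point is inferred.** Section 12.G.5.3 does not say month 6. The inference from 12.C.1 is strong but should be called one. The durable response at 3, 9 or 12 months would not cure the problem, because the 9- and 12-month readings come later still.
- **The overlap is about one scan interval.** Scan progression before month 3 does not count, "with progression being defined only AFTER the first 3-month staging evaluation". The next scheduled scan is at month 6, within 7 days of the visit that includes the leukapheresis (section 9.M). Most countable early progressions would surface around the draw, before new therapy could alter the reading. If only a quarter of early progressors lose 25-50% of their positive readings (q = 0.0625 to 0.125), the simple illustration falls to about 1.05-1.17. The exceptions are clinically indicated imaging, a switch to other therapy before month 6, and draws moved to standard-of-care visits.
- **Early deaths are largely covered.** A reader might infer from the default in 12.C.1, which makes anyone not meeting the criteria a non-responder, that patients who die before month 6 are coded negative. Section 12.C.2.6 points the other way: without a month-6 assessment they are not evaluable. What is missing is the link to 12.G.5.3.
- **The analysis is exploratory and imprecise.** With 28 patients split evenly and 48% progression-free, SE(log OR) = √[2(1/6.72 + 1/7.28)] = 0.757, so the 95% interval extends about exp(1.96 × 0.757) = 4.4-fold each way. A bias of 1.2-1.9 lies well inside that. This limits the practical impact but does not make a positive estimate interpretable.

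A stronger inference would be that the planned odds ratio *will be* inflated by 1.2-1.9. The documents do not support it: they give neither the size nor the direction of any effect of progression on the assay. That range also uses a single 50% response rate instead of the arm-adjusted 25%/75% design. Nor can the 50% progression expected at 3 months (section 6.B) serve as the early failure rate, because it is measured against pre-treatment scans and is not used to define progression.

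**Conclusion.** The timing problem is real and conditional. As 12.G.5.3 reads with 12.C.1, some failures precede or coincide with the covariate, and no landmark or rule for these patients is planned. The odds ratio is biased above 1 if progression by month 6, or the therapy after it, lowers the month-6 reading. It is unbiased if the reading is unaffected, or if affected patients are left out as unevaluable irrespective of their response. The 1.2-1.9 range, and the arm-specific 1.1-3.7 at q = 0.5, rest on assumed values of *f*, *m* and *q* and show only what could happen. The matter concerns the interpretation of one exploratory model in about 28 patients. It merits correction because the remedy is cheap and the result may inform later trials.

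**What to change.** In section 12.G.5.3:

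1. State that the covariate is the month-6 immune response of 12.C.1, and that the analysis set is patients evaluable for immune response under 12.C.2.6.
2. Add a month-6 landmark logistic model. Include patients alive and progression-free at the month-6 assessment; take progression or death from then to month 12 as the outcome, with arm and month-6 response as covariates.
3. Base any biomarker conclusion on the landmark model. Report the planned model beside it as a descriptive association with 1-year PFS.

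This needs SAP wording and analysis work only, with no new data. Of 28 evaluable patients, about 25 remain if 10% progress by month 6, 20 if 30% do, and 14 if 50% do. The interval is wider, and a two-covariate logistic model may be unstable at the lower end. The landmark also asks a narrower question: it cannot show any association with events before month 6, which is why the planned model should still be reported.

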High-throughput immunoblot (HTI): A secondary objective of the study will be to determine if patients treated develop “off-target” prostate cancer antigen-specific immune responses as evidence of antigen spread. Exploratory studies will evaluate T-cell responses to non-targeted antigens. However, the primary evaluation will be to evaluate IgG responses to a panel of prostate-associated antigens as we have previously reported in patients treated with vaccines or other immune-modulating agents [54-56]. IgG specific for 126 antigens, including 29 cancer-testis antigens [57, 58] and 97 prostate antigens frequently immunologically recognized [59-62] will be identified by screening a high-density phage array expressing these individual antigens, as we have previously reported [54, 56, 57]. The primary analysis will be conducted using sera obtained at 6 months, and compared with IgG responses identified at baseline, to determine whether IgG specific for individual antigens are elicited over time. Other time points will be assessed to determine the durability and kinetics of immune response development, and confirmatory ELISA studies will be performed if feasible.

REPORTING AND RESPONSE DEFINITION: A positive IgG response will be defined as an immunoreactive spot to a defined antigen, scored by at least 3 of 4 independent reviewers, and detectable to at least 2 of 3 replicates per immunoblot membrane. An IgG response resulting from immunization will be defined as an immunoreactive antigen identified at the 6-month (or other post-treatment time for subsequent analyses) time point that was not identified at the pre-treatment time point.

B. Circulating Tumor Cell (CTC) Enumeration

CTC will be enumerated at the same time points as for immune evaluation (pre-treatment, after 6 weeks, and at quarterly intervals for up to one year) using an ELISPOT methodology as described above, however using capture and detection antibodies specific for PSA [63]. This methodology has been used to count PSA-secreting cells directly from peripheral blood with a frequency < 1 per million PBMC. Given the rarity of these cells, they will not be normally distributed among individual wells of an ELISPOT plate. Hence, PBMC will be plated at

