This a pilot trial to evaluate the immunological and clinical effect of booster immunizations with a DNA vaccine encoding PAP with rhGM-CSF adjuvant following treatment with sipuleucel-T. The rationale for conducting this trial is summarized in Section 2 (E).

B. Objectives

The primary objective of this study is to evaluate whether immunization with a DNA vaccine encoding prostatic acid phosphatase (PAP, pTVG-HP) can augment PAP-specific effector and memory T cells following treatment with sipuleucel-T.

The secondary objectives are:

1. To determine 12-month progression-free survival
2. To determine median time-to-progression as a function of baseline time point (pretreatment or 3-months post treatment)
3. To evaluate effects of treatment on changes in serum PSA level and changes in PSA doubling time

The laboratory and clinical exploratory objectives are:

1. To determine overall survival

2. To evaluate effects of treatment on number of circulating tumor cells as determined by PSA ELISPOT
3. To evaluate PAP-specific antibody and T-cell immune responses following treatment with sipuleucel-T and DNA vaccine
4. To determine whether PAP-specific immune response is associated with prolonged (1 year) progression-free survival
5. To determine whether baseline immune responses (Th1 type or regulatory type) predict for immune responses elicited/augmented following treatment with sipuleucel-T +/- DNA vaccine
6. To determine whether treatment elicits immunologic antigen spread to other prostate associated antigens

C. Definitions/Endpoints

C.1. Primary Immunological Endpoint: Immune Response

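### The antigen-spread rule (at least 1 of 126 antigens newly scored at month 6) does not separate spread from turnover between visits, and no planned test estimates the effect of adding the DNA vaccine on spread

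*Combined protocol and SAP*

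**What the plan says.** Objective 6 in Sections 3.C and 12.B is "To determine whether treatment elicits immunologic antigen spread to other prostate associated antigens". Both sections list it as exploratory, although Section 10.A.5 calls it secondary.

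Section 10.A.5 describes the assay, a phage immunoblot for "IgG specific for 126 antigens, including 29 cancer-testis antigens [57, 58] and 97 prostate antigens frequently immunologically recognized". A spot is positive when it is "scored by at least 3 of 4 independent reviewers, and detectable to at least 2 of 3 replicates per immunoblot membrane". A response is attributed to immunization when the antigen is identified at a post-treatment "time point that was not identified at the pre-treatment time point". Other time points are read for durability and kinetics, and "confirmatory ELISA studies will be performed if feasible".

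Section 12.G.5.5 first plans a descriptive analysis of spread and of the antigens recognized. It then adds a logistic regression, whose stated purpose is to see whether spread goes with PAP-specific response. The outcome is set at one antigen: "The dependent variables will be the detection of IgG responses to ≥ 1" off-target antigen. The rest of the specification reads "antigen at 6 months (and not present pre-treatment) while treatment arm and 6-month PAP-specific immune responses (no vs. yes) will be included as covariates".

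Neither section counts antigens present at baseline and absent at month 6. Neither gives a background rate, a repeat pre-treatment sample, or a comparison of spread between arms without PAP response in the model.

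**The concern.** There are two separate difficulties.

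The first is the outcome. It counts gains only, over a large panel, with a threshold of one. Every antigen is an opportunity for a chance change between two samples taken about six months apart, and a single change makes the patient positive. The plan has no internal measure of how often that happens. Both arms receive sipuleucel-T, so there is no untreated arm to supply one.

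The second is the estimand. The heading of Section 12.G.5.5 asks whether treatment elicits spread, but the only model beneath it conditions on 6-month PAP response. That variable is measured after randomization and is the trial's primary endpoint. If the vaccine produces spread partly by way of PAP response, the arm coefficient leaves that part out.

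At stake is the interpretation of an exploratory biomarker that Section 2.E hopes will inform later studies. A raw proportion with spread could be read as biology when some of it is turnover. An arm coefficient near zero could be read as no vaccine effect on spread when the model was not built to estimate that effect.

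**Working it through.** The plan states no power, background rate or expected spread rate for this analysis, so there is no figure to reproduce.

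**Inputs from the documents.** Panel of 126 antigens (29 + 97) and the month-6 rule: Section 10.A.5. Threshold of one new antigen and model covariates: Section 12.G.5.5. 14 evaluable patients per arm and anticipated PAP response of 25% (Arm 1) and 75% (Arm 2): Section 12.F. Two-sided 5% level for this analysis: Section 12.G.1.

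**Assumed inputs.** The chance *q* that one antigen reads new at month 6 with no true change; independence across antigens; and the illustrative spread rates below.

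**Step 1: chance-positive patients.** P(at least 1 of 126) = 1 − (1 − q)^126.

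| q per antigen | Chance-positive patients | Expected among 28 |
|---|---|---|
| 0.05% | 6.1% | 1.7 |
| 0.1% | 11.8% | 3.3 |
| 0.2% | 22.3% | 6.2 |
| 0.5% | 46.8% | 13.1 |
| 1% | 71.8% | 20.1 |

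Holding chance positives to 5% needs q ≤ 1 − 0.95^(1/126) = 0.041%. Half of all patients are positive by chance at q = 1 − 0.5^(1/126) = 0.55%. If only the 97 prostate antigens are counted, the shares at q = 0.1%, 0.5% and 1% are 9%, 39% and 62%.

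**Step 2: dilution of an arm contrast.** With true spread *s* and chance-positive share *b* from step 1, the observed rate is 1 − (1 − s)(1 − b). Assume true spread of 10% and 50%. Power is for an exact unstratified Fisher comparison, two-sided 5%, 14 per arm.

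| q | Observed, Arm 1 | Observed, Arm 2 | Power |
|---|---|---|---|
| 0 | 10% | 50% | 54% |
| 0.1% | 20.7% | 55.9% | 35% |
| 0.5% | 52.1% | 73.4% | 12% |
| 1% | 74.6% | 85.9% | 5% |

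If true spread is equal in the arms, the observed rates stay equal. Turnover of this kind costs power but does not bias the comparison under the null.

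**Step 3: what the arm coefficient estimates.** Take the planning PAP response rates of 25% and 75%. Assume spread of 60% in PAP responders and 20% in non-responders, whatever the arm.

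- Arm 1: 0.25 × 0.60 + 0.75 × 0.20 = 30%
- Arm 2: 0.75 × 0.60 + 0.25 × 0.20 = 50%
- Total odds ratio: (0.50/0.50) / (0.30/0.70) = 2.33
- Arm odds ratio given PAP response: 1.0

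The last figure is 1.0 by construction, because the example sends the whole effect through PAP response. It shows that the two quantities can differ; it does not predict the trial's result.

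**The case against.** The strongest reply is that Section 12.G.5.5 does what it says. It answers the objective descriptively and assigns the model a different question, association with PAP response. In that model PAP response is the exposure and arm is the adjustment, so the arm coefficient was never offered as the treatment effect. This stands. A reader might infer that objective 6 cannot be answered, and the documents do not support that: the descriptive analysis is planned, and an unadjusted table by arm could be made from the same data. What remains is that no such comparison is specified, under a heading that asks about treatment.

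The assay also has real safeguards: agreement of reviewers and replicates, later time points, and ELISA where feasible. These may well keep q low. They act on false spots within a blot, however, and ELISA is outside the response definition, so none of them measures change between visits.

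The size is unknown. At q of 0.04% or less the problem is small, and positive correlation between antigens in one serum would generally lower the chance of at least one at the same q.

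Finally, mediation is not established. PAP response here is a T-cell endpoint and spread is an IgG readout; the plan treats their link as something to test.

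**Conclusion.** The point holds in a limited form. The definition of spread cannot tell a true new response from turnover between visits, and no planned test estimates the total effect of adding the DNA vaccine on spread.

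The first part has a size only under assumption: from about 6% chance-positive patients at q = 0.05% to about 72% at q = 1%, with independent antigens. A reader might infer that most patients in both arms will be labelled positive and that the outcome will saturate. That needs q above about 0.55%, and nothing in the documents shows that it is so high, or that it is low enough to ignore.

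The second part needs no assumption about q. It follows from conditioning on a post-randomization variable. How far the adjusted and total effects differ depends on how much of any effect runs through PAP response, which is unknown.

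This is a worthwhile improvement to an exploratory analysis in a pilot trial. It does not touch the primary immune-response comparison or any safety conclusion.

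**What to change.** Amend Section 12.G.5.5 as follows.

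1. Keep the logistic model for the association between spread and PAP response only, and state that its arm coefficient is not the effect of treatment on spread.
2. Report for each patient the number of antigens gained and the number lost between baseline and month 6, using the scoring rule of Section 10.A.5 for both.
3. Compare gains with losses within patients, for example by a signed-rank test on net gain. If nothing changes and the assay is equally sensitive at both visits, expected gains equal expected losses, so losses serve as an internal control. This matters because both arms receive sipuleucel-T. It removes symmetric turnover, but not changes due to the disease itself over six months.
4. Compare net gain between arms with a rank-sum test stratified by predicted survival and not adjusted for PAP response. Section 12.G.5.1 already plans a stratified rank-sum test for circulating tumor cells.

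Raising the threshold to two antigens would be simpler, but its benefit still depends on the unknown rate: chance positives fall from 11.8% to 0.7% at q = 0.1%, but only from 71.8% to 35.9% at q = 1%.

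The cost is a change of wording. The loss counts come from the baseline and month-6 blots already planned, so no new assays are needed. The downside is one more exploratory comparison in a plan that makes no adjustment for multiplicity.
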